7.7.1. Trial assessments, sub-study only

Pulse wave velocity: (PWV) is a non-invasive assessment to measure arterial stiffness, which is a surrogate marker that predicts cardiovascular events. PWV is defined as the speed of which the pulse wave travels along a length of artery, expressed in m/s, where higher values indicate higher cardiovascular risk (Oliver et al. 2003). PWV will be measured using the carotid-femoral technique, which is regarded as the gold-standard to measure large artery stiffness (Van Bortel et al. 2012). This is done using a device called the SphygmoCor® Xcel (AtCor Medical UK). The SphygmoCor® Xcel will calculate the distance

divided by pulse transit time between carotid and femoral, provided by a tonometer over the carotid artery, and a blood pressure cuff over the femoral artery (Butlin et al. 2017).

Iontophoresis and full-field laser perfusion imaging (FLPI): Iontophoresis is a non-invasive method that drives ionised medications across the skin with the use of a small amount of physiologically acceptable electric current (0.5 mA/cm² or less). This is performed using a set of electrodes, and one of which contains an ionised medication in a chamber. When electric current is applied, it will move the ionised medication from one electrode to another (Dhote et al. 2012). The medication can be a vasoactive compound such as acetylcholine (positive charged) or sodium nitroprusside (negative charged), which can then be used to assess vasodilation. An impairment in response to acetylcholine during iontophoresis implies endothelial dysfunction (Schonberger et al. 2006).

Full-field laser perfusion imaging (FLPI) measures the blood flow within the superficial microcirculation using laser speckle contrast imaging. FLPI uses a near infra-red laser diode (785nm) to illuminate the skin, and captures images of the superficial micro vessels at a depth of 300µm. The movement of red blood cells within the skin and tissues will cause the laser light to backscatter. The backscattered light will then get focussed through a limiting aperture and captured by a camera, creating speckle patterns. The speckle pattern is altered by movements of the red blood cells, and can be converted into a colourised image that represents blood flow within a region of tissue in real time (Adams 2014). FLPI can be combined with iontophoresis of vasoactive medications to provide an assessment of endothelial dysfunction.

Waist and hip measurement will be taken as the ratio of these measurements are useful predictors of heart attacks and strokes.

7.8. Long term follow-up assessments

Nil

7.9. Quality of life and symptom assessments

Quality of life will be evaluated using the QOL-B respiratory symptom scale (Quittner et al. 2015a) and the BIM.

Participants will complete a daily diary of symptoms BEST during the 28 day treatment period. This is completed at home either on paper and brought to the research visit or entered electronically via weblink or mobile application.

7.10. Withdrawal criteria

Participants are free to withdraw at any time and are not obliged to give reason(s). The CI, PI or delegate will make a reasonable effort to ascertain the reason(s), both for those who express their right to withdraw and for those lost to follow up, while fully respecting the individual's rights.

The investigator may withdraw a patient at any time if it is in the best interest of the patient and treatment continuation would be detrimental to the patient's well-being. A full explanation will be provided. If the trial is being conducted on an intention to treat basis, and the participant has been randomised and given one or more doses of IMP, s/he will be asked to complete trial visits as per the protocol, if the CI considers it appropriate. This would allow

for an intention to treat analysis - but will be censored in the per-protocol analysis. Participants are free to refuse to do so. Withdrawn participants will not be prescribed IMP.

Those withdrawn, including those lost to follow-up, will be identified and a descriptive analysis of them provided, including the reasons for their loss, if known, and its relationship to treatment and outcome.

7.11. If a participant withdraws or is withdrawn, they have the right to ask for their data and samples held to be removed/disposed of, changed or deleted. This might not always be possible if it means the data/samples cannot be used to do the research, if this is the case, participants will be informed. Storage and analysis of clinical samples

The collection, processing and storage of samples will be detailed in the Laboratory Manual. The analysis of samples will be detailed in the Laboratory Analytical Plan.

Blood and sputum samples will be obtained as per Laboratory Manual. Processing of blood for serum generation and cell isolation will be completed at sites, details of how processing will be carried out will be included in the Laboratory Manual. The resulting serum, sputum supernatant, whole sputum and cells will be stored at site.

All samples will be stored at sites and transferred to the UoD, Division of Molecular and Clinical Medicine, for analysis and storage either at the end of site's participation or sooner if site requests. Access to samples will be limited to members of the CI's laboratory team. Specimens will be registered with NHS Tayside Biorepository. Future use of those specimens will be made available and will be governed by the NHS Tayside Biorepository and access committee. Trial data may be released with samples.

It is the responsibility of the trial site to ensure that samples are appropriately labelled in accordance with the trial procedures to comply with the Data Protection Act 2018. Biological samples collected from participants as part of this trial will be transported, stored, accessed and processed in accordance with national legislation relating to the use and storage of human tissue for research purposes and such activities shall at least meet the requirements as set out in the 2004 Human Tissue Act and the 2006 Human Tissue (Scotland) Act.

7.12. End of trial

The end of trial at all sites is defined as last participant last visit (LPLV). The Sponsor, CI and/or the TSC have the right at any time to terminate the trial for clinical or administrative reasons.

The end of the trial will be reported to the Sponsor, Research Ethics Committee (REC), Medicines and Healthcare products Regulatory Agency (MHRA) and National Health Service Research & Development (NHS R&D) Office(s) within 90 days, or 15 days if the trial is terminated prematurely. The CI will ensure that any appropriate follow up is arranged for all participants.

A final clinical trial report will be submitted to the MHRA within 1 year of the end of the trial and will also be provided to the Sponsor and REC.

8. TRIAL TREATMENTS

8.1. Name, description and regulatory status of investigational medicinal products (IMPs) for open arms

	Treatment	Dosage, form and strength	Regulatory status
Arm 2	Disulfiram	400 mg oral tablets two 200mg tablets once daily	Not approved for the treatment of bronchiectasis. Has current marketing authorisation (MA) in the UK for use as an adjuvant in the treatment of drinking problems.
Arm 3	Dipyridamole	200mg oral prolonged/modified release capsule one capsule twice daily	Not approved for the treatment of bronchiectasis. Has current MA in the UK for use in secondary prevention of ischaemic stroke and transient ischaemic attacks and as an adjunct to oral anti-coagulation for prophylaxis of thromboembolism associated with prosthetic heart valves.
Arm 4:	Doxycycline	100mg oral capsule one capsule once daily	Not approved for the treatment of bronchiectasis. Has current MA in the UK for use in the treatment of a variety of infections caused by susceptible strains of Gram-positive and Gram-negative bacteria and certain other micro-organisms.

8.2. Name, description and regulatory status of IMP(s) for closed arms.

Nil, initial trial protocol, no treatment arms have been closed.

8.3. Product Characteristics

The reference safety information (RSI) is described in Section 9.4.

8.4. Accountability Procedures

The PI or delegated trial staff will maintain an accurate record of the receipt and dispensing of the IMP in a drug accountability log. Monitoring of drug accountability will be performed as per Sponsor Monitoring Plan.

8.5. Preparation and labelling of IMP

IMP stock will be taken from local hospital supply. The IMP will be labelled by delegated pharmacy staff, as per the pharmacy manual.

8.6. Drug supply and storage, open treatment arms

Where a site has difficulty obtaining the supply of medication for any of the treatment arms, the site will continue to recruit and randomise participants between the available treatment arms and usual care at that site.

	Treatment	Supply	Storage
Arm 2	Disulfiram	Generic drug, procured through site NHS pharmacy	As per summary of product characteristics (SmPC) conditions
Arm 3	Dipyridamole	Generic drug, procured through site NHS pharmacy	As per SmPC conditions
Arm 4	Doxycycline	Generic drug, procured through site NHS pharmacy	As per SmPC conditions

8.7. Dosage schedules, open treatment arms

	Treatment	Dosage schedule	Duration
Arm 2	Disulfiram	Two 200mg tablets once daily	28 days
Arm 3	Dipyridamole	One 200mg capsule twice daily	28 days
Arm 4	Doxycycline	One 100mg capsule once daily	28 days

8.8. Dosage modifications, open treatment arms

	Treatment	Dosage modifications
Arm 2	Disulfiram	Nil
Arm 3	Dipyridamole	Nil
Arm 4	Doxycycline	Nil

8.9. Known drug reactions and interaction with other therapies, open treatment arms

Treatment	Known drug reactions	Known drug interactions
-----------	----------------------	-------------------------

Arm 2: Disulfiram
	
Disulfiram-alcohol reaction
	
Alcohol - Disulfiram has several CYP450 enzyme interactions, which results in the interference of the metabolism of various drugs. Disulfiram inhibits CYP2E1 CYP1A2, and is activated by CYP3A4. Amitriptyline – increased disulfiram alcohol reaction Chlorpromazine – increased disulfiram alcohol reaction Benzodiazepines – enhanced sedative effect Phenytoin – increased phenytoin concentration and needs dose adjustment Warfarin – increased anticoagulant effect and needs dose adjustment Rifampicin – increased concentration due to reduced metabolism and renal excretion Metronidazole, Isoniazid and Paraldehyde were anecdotally found to increased risk of psychotic reaction

Arm 3: Dipyridamole
	
Very common, $\geq 1/10$ Headache Dizziness Diarrhoea Nausea
 
Common, $\geq 1/100$ to $< 1/10$ Rash Angina pectoris Vomiting Myalgia
 
Unknown drug reactions are detailed in the RSI.
	
Adenosine - Dipyridamole inhibits the uptake and degradation of adenosine in the blood vessels and cells. Adenosine use should be adjusted or avoided. Antiplatelets and anticoagulation – increases bleeding risk. Antihypertensives – increases risk of hypotension. Alcohol – increase the risk of hypotension. Cholinesterase Inhibitors in Myasthenia Gravis – worsens symptoms

Arm 4: Doxycycline
	
Common, $\geq 1/100$ to $< 1/10$ Hypersensitivity Headache Nausea/vomiting Photosensitivity reaction, rash including maculopapular and erythematous rashes
 
Uncommon, $\geq 1/1000$ to $< 1/100$ Vaginal infection Dyspepsia
 
Rare and unknown drug reactions are detailed in the RSI.
	
Antacids – may impair absorption of doxycycline Barbiturates, Carbamazepine, phenytoin, and primidone – may reduce exposure to doxycycline Warfarin - increased anticoagulant effect and needs dose adjustment. Oral contraception – few cases of breakthrough bleeding or pregnancy Alcohol – reduced doxycycline half-life Retinoids – increased risk of benign intracranial pressure Rifampicin - may reduce exposure to doxycycline

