6.3.2. Arm 3: Dipyridamole

- Currently on Dipyridamole (patients should have a washout period of at least 30 days from last dose if they have previously received this medication)
- Hypersensitivity to Dipyridamole
- Participant, or investigator, objects to randomisation to Dipyridamole
- Currently on dual antithrombotic therapy (aspirin or P2Y12 inhibitor plus anticoagulation)
- Current on direct oral anticoagulants (Dabigatran, Rivaroxaban, Edoxaban, Apixaban, Betrixaban or drugs in the same class) or long-term warfarin
- Any major trauma or haemorrhage including gastrointestinal bleeding, operation within the past 30 days
- Coagulation disorder
- Severe coronary artery disease (unstable angina, recent myocardial infarct in 30 days, decompensated/unstable severe left systolic dysfunction, uncontrolled heart failure)
- Myasthenia gravis

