Spirometry: post bronchodilator spirometry at visits will be carried using American Thoracic Society/European Respiratory Society's guidelines. Forced Expiratory Volume (FEV1) forced vital capacity (FVC) and Forced Expiratory Flow at 25-75% (FEF25-75) will be measured.

Questionnaires: as per schedule of procedures.

Blood samples: collected, processed, and stored as per laboratory manual. Full blood count, urea and electrolytes, liver function tests will be analysed by the local NHS laboratory. Samples will also be taken for trial outcomes. Additional blood samples will be collected for future biomarker and molecular microbiology research, dependent on participant consent, see section 7.2.1. A maximum of 100 ml of blood will be obtained at any visit.

Sputum sample: a sputum sample will be collected, processed, divided and stored as per laboratory manual. Participants will be asked to bring a spontaneous early morning sputum sample with them to visits from their second visit onwards. Where a participant is unable to produce a sputum sample at a visit a hierarchical approach to obtaining sputum samples will be used:

1. spontaneous sputum sample produced at the visit
2. spontaneous early morning sputum brought from home on the day
3. spontaneous early morning sputum brought in within the following 48 hours after the scheduled visit.
4. Induced sputum at sites able to perform induced sputum according to local protocols.

A sputum sample will be analysed locally for active neutrophilic inflammation at screening/baseline using NEATstik.

A sample will also be taken for trial outcomes. Additional sputum sample will be taken for future biomarker and molecular microbiology research, see section 7.2.1.

Nasal sample: brushing of the inferior turbinate will be performed to obtain nasal epithelial cells and the brush then placed into media for storage. Participants should not have a nasal brushing performed if they are receiving anticoagulants (Oral anticoagulants or warfarin) or have a history of deviated nasal septum, base of skull fracture or severe epistaxis. If any of these are present the nasal brushing will be omitted.

Safety assessments: participants will be requested to attend an unscheduled visit if they experience a bronchiectasis exacerbation or any other safety concern.

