8.11. Trial restrictions

	Treatment	Trial restrictions
All arms		To avoid contamination between the arms, participants who develop an exacerbation during the study and require antibiotic treatment should receive an antibiotic other than doxycycline. If participants are not able to safely avoid doxycycline during the trial period they should not be enrolled in the study.
Arm 2	Disulfiram	Alcohol Participants will be required to consent to not consuming alcohol for duration of treatment and at least 14 days after stopping treatment. Written advice will be provided to participants about how to avoid products containing alcohol during the trial period.
Arm 3	Dipyridamole	Participants should not commence new oral anticoagulant drugs during the trial period. Participants needing to initiate anticoagulants should withdraw from the study.
Arm 4:	Doxycycline	No restrictions. Exacerbations of bronchiectasis should be treated with an alternative antibiotic.
All	Nasal brushing	Participants should not have a nasal brushing performed if they are receiving anticoagulants (oral anticoagulants or warfarin) or have a history of deviated nasal septum, base of skull fracture or severe epistaxis. If any of these are present the nasal brushing will be omitted. This will not affect their participation in the trial.

WOCBP must be willing to have pregnancy testing prior to trial entry and at each research visit, unless the participant has been randomised to usual care.

A woman is considered of childbearing potential, i.e. fertile, following menarche and until becoming post-menopausal unless permanently sterile. A post-menopausal state is defined as no menses for 12 months without an alternative medical cause (including use of hormone replacement therapy).

In addition, WOCBP must be willing to use a form of a medically approved birth control method throughout the trial (and for minimum of 4 weeks after last dose), unless randomised to usual care, which include:

- combined (estrogen and progestogen containing) hormonal contraception associated with inhibition of ovulation:
 - oral
 - intravaginal
 - transdermal
- progestogen-only hormonal contraception associated with inhibition of ovulation:
 - oral
 - injectable
 - implantable
- intrauterine device (IUD)
- intrauterine hormone-releasing system (IUS)

- bilateral tubal occlusion
- vasectomised partner

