Gastrointestinal Disorder	People on doxycycline commonly experience gastrointestinal symptoms which are generally mild to moderate, including nausea, abdominal pain, vomiting, and diarrhoea. Doxycycline may also cause oesophageal inflammation or ulcers. It is considered that long oesophageal transit time and dehydration contributes to nausea and mucosal inflammation related to doxycycline. (Tan et al. 2011).	- Participants are advised to ingest the pill in an upright position, with plenty of fluid, and avoid taking before bedtime.
Disulfiram 400mg		
Disulfiram-Ethanol Reaction	Disulfiram-Ethanol Reaction (DER) mostly occurs in the first 12 hours after administration. Although severity of the DER is related to the disulfiram dose and ethanol intake, it was also seen in cases with blood alcohol as low as 10mg/100ml. A study found 19% of patients on disulfiram experienced DER while using alcohol-based hand sanitizer. (Lanz et al. 2023).	- Participants randomised to Disulfiram will be advised to abstain from alcoholic beverages or the use of any alcohol-based products during intervention - Proper ventilation during administration may alleviate DER when using alcohol based hand sanitizer
Hepatotoxicity	Carbon disulfide is released during hepatic disulfiram metabolism, and can cause hepatocellular degeneration or necrosis. Hepatotoxicity have previously manifested in the form of asymptomatic transaminitis to rare fulminant hepatic failure. This may be attributed to pre-existing alcoholic liver condition, but also found in 25% patients with	- Regular clinical and laboratory monitoring for hepatotoxicity

	no previous alcohol misuse. Most of these effects are reversible when Disulfiram is stopped. (Lanz et al. 2023).	
Dipyridamole		

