Headache	
Headaches are a well-known transient side effects of dipyridamole, due to its vasodilatory properties. This often leads to discontinuation, as seen in 8% of patients who were enrolled into the dipyridamole arm in the Second European Stroke Prevention (ESPS2) Trial.
 
A bioequivalence trial comparing two different formulations of dipyridamole involving mostly young healthy adults found that 72% of volunteers reported at least one episode of headache over the course of two weeks. This bioequivalence trial also found that the volunteers are more likely to experience headache in the first week, 2-3 hours after the morning dose, and all volunteers recovered fully from the headaches regardless of severity. (Theis, Deichsel, and Marshall 1999)
	- Participants should be informed that they may experience transient headaches while initiating dipyridamole, and reassurance that it will improve with time.
Bleeding	
As an antiplatelet, patients may be at a higher risk of bleeding complications. Adding dipyridamole to anticoagulation increases the risk of bleeding by about 50% (Massel and Little 2013).
 
However, for patients not on anticoagulation, this risk was not seen in the large clinical trials performed in patients who had a Stroke or Transient Ischaemic Attack (TIA). In
	
- Participants who are on dual antiplatelet, any anticoagulant, or any coagulopathy should not be randomised to dipyridamole. Participants who are already on Aspirin are safe to be recruited.
 
- Participants who recently had any gastrointestinal bleeding, head trauma, or major operation within 30 days should not be randomised to dipyridamole

	ESPS2, patients who were randomised to placebo (n=1649) and dipyridamole alone (n=1654) reported similar events for bleeding any site, 74 and 77 respectively. ESPS2 also found that the bleeding risk between Aspirin (n=1649) and Aspirin plus Dipyridamole (n=1650) are similar at 135 and 144 events respectively (Diener et al. 1996).	

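### Section 8.9 says warfarin needs dose adjustment with disulfiram and doxycycline, but no eligibility, restriction, risk or monitoring rule for Arms 2 and 4 carries this out

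*Protocol*

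**What the plan says.** The interaction table in section 8.9 carries the same warfarin entry for disulfiram and for doxycycline: "increased anticoagulant effect and needs dose adjustment". Section 8.8 allows no dose modification of any trial drug, so the adjustment can only be made to the warfarin.

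For dipyridamole (Arm 3) the protocol has explicit rules. Section 6.3.2 excludes people on direct oral anticoagulants, "drugs in the same class) or long-term warfarin". Section 8.11 adds "Participants should not commence new oral anticoagulant drugs during the trial period". Appendix 1 gives the mitigation: "Participants who are on dual antiplatelet, any anticoagulant, or any coagulopathy should not be randomised to dipyridamole".

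For Arm 2, section 8.11 deals with alcohol only. For Arm 4 it reads "No restrictions. Exacerbations of bronchiectasis should be treated with an alternative antibiotic". Section 8.11 also tells sites to omit nasal brushing in participants "if they are receiving anticoagulants (oral anticoagulants or warfarin"), and says that this does not affect their participation.

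On laboratory safety tests, section 7.7 says "Full blood count, urea and electrolytes, liver function tests will be analysed by the local NHS laboratory". Appendix 4 schedules that panel at screening, days 14, 28 and 56, and safety visits.

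**The concern.** The protocol identifies a hazard and names the action it calls for, but does not say who acts, when, or on what information. A warfarin user can meet every written criterion for Arm 2 or Arm 4 and start treatment. No INR is required, and whoever doses the warfarin need not be told.

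The main risk is over-anticoagulation after the trial drug starts, in a disease whose features, according to the Background, include occasional haemoptysis. A second risk is conditional: if the warfarin dose is lowered for the 28 treatment days, it has to be raised again once the trial drug stops. This is a participant-safety matter, not an inferential one.

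**Working it through.** The protocol gives no figure to reproduce. The check is a comparison of sections, followed by one piece of arithmetic from the allocation rule.

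**Sections compared for warfarin, anticoagulants, INR or clotting tests**

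- General exclusions (6.2): nothing.
- Arm-specific exclusions: Arm 2 (6.3.1) nothing; Arm 3 (6.3.2) direct oral anticoagulants and long-term warfarin; Arm 4 (6.3.3) nothing.
- Interactions (8.9): Arm 2, warfarin dose adjustment needed; Arm 3, more bleeding with antiplatelets and anticoagulants; Arm 4, warfarin dose adjustment needed.
- Concomitant medication (8.10): recorded in a log, with no action on interactions.
- Restrictions (8.11): Arm 2 alcohol only; Arm 3 no new oral anticoagulants; Arm 4 none beyond using another antibiotic for exacerbations.
- Appendix 1: the disulfiram rows cover the alcohol reaction and hepatotoxicity, the doxycycline rows photosensitivity and gastrointestinal effects. The only bleeding row is under dipyridamole.
- Appendix 4: no INR or clotting test at any visit.

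The protocol does turn a known disulfiram risk into monitoring elsewhere. Appendix 1 sets "Regular clinical and laboratory monitoring for hepatotoxicity", and the liver tests in the local panel serve it. The warfarin entry has no counterpart.

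**Can a warfarin user enter?** Yes. No general exclusion applies, and the nasal-brushing rule provides for anticoagulated participants. It does not show how many there would be, or in which arm.

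**Nominal chance of an interacting drug**

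Inputs: equal randomisation among the open arms for which the person is eligible (7.3); four arms open (usual care, disulfiram, dipyridamole, doxycycline); long-term warfarin bars dipyridamole (6.3.2).

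- Eligible for all other arms: 4 − 1 = 3 arms remain, of which 2 interact. Chance = 2/3 = 67%.
- Disulfiram also barred, for example by previous stroke or coronary artery disease (6.3.1): 2 arms remain, of which 1 interacts. Chance = 1/2 = 50%.

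These are upper figures for such a person. They assume that no investigator objects and that the site can obtain both drugs (8.6 allows for supply gaps), and they ignore small shifts from minimisation.

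**The case against.** **Section 8.9 is itself an instruction, and clinicians are involved throughout.** A medically qualified person assesses eligibility (7.1.2). An investigator may object to either arm before randomisation (6.3.1, 6.3.3). Medication is reviewed at every visit, including day 7 (7.7). The allocation goes to the trials pharmacy (7.3.1), the medical record is flagged (11.1), and unscheduled safety visits are available. The data monitoring committee reviews safety after the tenth participant in each arm reaches day 28 (10.4). This stands in part: entry is subject to medical judgement. But none of these steps mentions warfarin, requires an INR or requires notice to the warfarin prescriber, and the committee review comes too late for an individual starting treatment.

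**Arm 3.** A reader might infer that the protocol contradicts itself by excluding warfarin in Arm 3 only. The text does not support that. For dipyridamole, 8.9 offers no dose remedy, and Appendix 1 puts the added bleeding risk with anticoagulation at about 50%, so exclusion is a reasonable response. For the other two drugs, 8.9 names a remedy. Excluding in one arm and managing in the others is coherent. Arm 3 shows only that an explicit rule is feasible.

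**Warfarin is singled out.** Other 8.9 interactions, such as benzodiazepines or rifampicin with disulfiram and carbamazepine with doxycycline, also lack a matching rule. True, but in Arms 2 and 4 the entries that say a co-medication's dose needs adjusting are warfarin and, for disulfiram, phenytoin. Phenytoin is presumably covered for the most part by the epilepsy exclusion in 6.3.1.

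**Unseen manuals.** A reader might infer that the trial has no INR provision at all. That goes too far: the pharmacy manual and trial guidelines are not shown, and nothing in the protocol displaces ordinary anticoagulation care. The protocol does not, however, point to either document for interactions.

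**Conclusion.** The point holds as a gap between a hazard stated in 8.9 and the rules for Arms 2 and 4. It is not an internal contradiction. A long-term warfarin user is kept out of Arm 3 only and nominally has up to a 2/3 chance of an interacting drug (1/2 if disulfiram is barred), subject to discretionary safeguards.

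The documents give neither the number of warfarin users nor any rate of bleeding or INR change, so expected harm cannot be sized. The number is probably small. A reader might also conclude that the trial must run its own fixed INR schedule. The documents give no basis for particular days, and such a schedule would add procedures that routine care can supply. What is missing is either an exclusion or a required notice.

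The primary estimate, the type I error rate and power are unaffected. This is an inexpensive safety improvement worth making.

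**What to change.** Choose one; the choice is a clinical decision for the sponsor.

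(a) **Exclude.** Add long-term warfarin to the exclusions in 6.3.1 and 6.3.3, a line in 8.11 for Arms 2 and 4 against starting warfarin during treatment, and matching rows in Appendix 1. Cost: an amendment, and the loss of the few long-term warfarin users, for whom only usual care would remain open among the present arms.

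(b) **Notify.** In 8.11, replace the Arm 4 statement of no restrictions and add to the Arm 2 entry, with the same text in Appendix 1: for participants on warfarin, inform the anticoagulation service of the trial drug start and stop dates before the first dose; INR monitoring and dose adjustment during and after treatment follow local practice. Keep the existing Arm 4 instruction on antibiotics for exacerbations. Cost: an amendment and one notification step per warfarin user, with no new trial visit or trial blood sample.
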